### **12.6.8.1 Subject withdrawal**

All enrolled subjects have the right to withdraw their consent at any time during this study. All data collected until the time of subject withdrawal will remain in the study database and will be used for analysis. Whenever possible, the site staff should obtain written documentation from the subject who wishes to withdraw his/her consent for future follow-up visits. If the site staff is unable to obtain written documentation, all information regarding the subject's withdrawal must be recorded in the subject's medical record. In addition, the appropriate eCRFs must be completed for the subject and clear documentation of the subject's withdrawal should be provided to the Sponsor.

### **12.6.8.2 Subject discontinuation by investigator**

An Investigator may discontinue a subject from the study, with or without the subject's consent, for any reason that may, in the Investigator's opinion, negatively affect the well-being of the subject. If a subject is withdrawn from the study, the Investigator will promptly inform the subject and Sponsor. If a subject is enrolled and undergoes attempted delivery with the Barrel VRD without successful implant of the investigational device, the subject will be exited from the study following the 30 day visit.

### **12.6.8.3 Lost to follow-up**

A subject will be considered lost to follow-up if the subject cannot be reached after three (3) attempts to contact the subject for the 1 year visit. The site must document a minimum of three (3) attempts, and the final documented attempt should be made via registered letter.

### **12.6.8.4 Discontinuation by IRB**

The IRB/EC may choose to discontinue the study at any center(s) for which they granted approval if:

- The research study is not conducted in accordance with the IRB/EC's requirements.
- The research study indicates unexpected serious harm to subjects.

### **12.6.8.5 Study Discontinuation by Sponsor**

The Sponsor may choose to discontinue the study should the Sponsor discover additional information during the study that may cause harm to subject safety.

If the study is terminated prematurely or suspended, the Sponsor will promptly inform all clinical Investigators of the termination or suspension and the reason(s) for this. The IRB/EC will also be informed, either by the Sponsor or Investigator if a local IRB/EC is utilized, promptly and provided with the reasons(s) for the termination. If applicable, regulatory authorities will be informed. Enrolled subjects will be asked to complete all remaining study visits and the subject will then be seen by the treating physician according to standard care following intracranial aneurysm treatment.

## 12.7 Angiography Core Lab

### 12.7.1 Assessments

The following assessments will be made by the Angiography Core Lab from images submitted from the sites. The images will be submitted by site with all subject identifiers removed and only the assigned subject study number on the images.

Procedural- pre, peri and post images

- Aneurysm location
- Raymond grade (pre-procedure required only for previously coiled aneurysms)
- Stenosis of parent and branch arteries (pre-procedure)

180 days  $\pm$  30 days post-procedure

- Stenosis of parent and branch arteries
- Raymond grade
- In-stent stenosis

12 months  $\pm$  8 weeks post-procedure

- Stenosis of parent and branch arteries
- Raymond grade
- In-stent stenosis

Unscheduled

- Stenosis of parent and branch arteries
- Raymond grade
- In-stent stenosis

## 12.8 Adverse Event Reporting

All adverse events will be collected during the course of the study on the eCRFs.

Adverse event status will be evaluated throughout the study. These will include events occurring from the point of consent until a subject exits the study. Investigators must obtain all information available to determine the causality and outcome of the AE and to assess whether it meets the criteria for classification as a serious and/or unexpected event requiring notification to the Sponsor, regulatory agency, and as applicable, IRB/EC, within the specified reporting timeframe. AEs will be categorized using the definitions in **Section 12.8.1**.

All study AEs, as well as the treatment and follow-up required, should be documented in the subject's medical records and in the eCRF. All study AEs will be followed by the Investigator until resolution or until the end of the 12 month follow-up. A list of potential anticipated adverse events is provided in **Section 13**.

All relevant medical conditions reported at screening/baseline visit will be recorded in the medical history form, including any signs and symptoms related to the condition of intra-cranial aneurysm.

### 12.8.1 Definitions

An **Adverse Event (AE)** is defined as any untoward medical occurrence, unintended disease or injury, or untoward clinical signs (including abnormal laboratory findings) in subjects, users or other persons, whether or not related to the investigational medical device. (ISO 14155:2011)

*Note 1:* This includes events related to the investigational device or the comparator.

*Note 2:* This includes events related to the procedures involved (any procedure in the clinical investigational plan).

*Note 3:* For users or other persons this is restricted to events related to the investigational medical device.

An **Adverse Device Effect (ADE)** is defined as an adverse event related to the use of an investigational medical device. (ISO 14155:2011) The investigational medical devices for this study are the Barrel® VRD, and the Reverse Medical® Detachment System.

*Note 1:* This includes any adverse event resulting from insufficiencies or inadequacies in the instructions for use, the deployment, the implantation, the installation, the operation, or any malfunction of the investigational device.

*Note 2:* This includes any event that is a result of a use error or intentional misuse of the investigational medical device.

A **Serious Adverse Event (SAE)** is defined as an AE that:

- a) Led to death,
- b) Led to serious deterioration in the health of the subject, that either resulted in
  1. A life-threatening illness or injury, or
  2. A permanent impairment of a body structure or a body function, or
  3. In-patient or prolonged hospitalization, or
  4. Medical or surgical intervention to prevent permanent life-threatening illness or injury or permanent impairment to a body structure or a body function,
- c) Led to fetal distress, fetal death or a congenital abnormality or birth defect (ISO 14155:2011)

*Note 1:* This includes device deficiencies that might have led to a serious adverse event if a) suitable action had not been taken or b) intervention had not been made or c) if circumstances had been less fortunate. These are handled under the SAE reporting system.

*Note 2:* A planned hospitalization for pre-existing condition, or a procedure required by the Clinical Investigational Plan, without a serious deterioration in health, is not considered to be a serious adverse event.

A **Serious Adverse Device Effect (SADE)** is defined as an adverse device effect that has resulted in any of the consequences characteristic of a serious adverse event. (ISO 14155:2011)

An **Unanticipated Serious Adverse Device Effect (USADE)** is defined as a serious adverse device effect which by its nature, incidence, severity or outcome has not been identified in the current version of the risk analysis report. (ISO 14155:2011)

*Note:* Anticipated: an effect which by its nature, incidence, severity or outcome has been previously identified in the risk analysis report.

An **Unanticipated Adverse Device Effect (UADE)** is defined as any serious adverse effect on health or safety or any life-threatening problem or death caused by, or associated with, a device, if that effect, problem, or death was not previously identified in nature, severity, or degree of incidence in the investigational plan or application (including a supplementary plan or application), or any other unanticipated serious problem associated with a device that relates to the rights, safety, or welfare of subjects. (21 CFR 812.3)

**Severity:**

- Mild: No limitation of usual activities, no therapy or only symptomatic therapy required to treat the injury or illness.
- Moderate: Some limitation of usual activities or specific therapy is required.
- Severe: Inability to carry out usual activities, hospitalization, emergency treatment, life threatening events, or death.

**Relatedness:**

- Study Disease-related: Event is clearly attributable to the underlying study disease state (aneurysm) or concomitant medications taken for these with no temporal relationship to the device, procedure, or concomitant medications.
- Concomitant disease-related: Event is clearly attributable to an underlying concomitant disease state or concomitant medication taken for these with no temporal relationship to the device, procedure/treatment, or study disease state.
- Procedure-related: Event has a strong temporal relationship to the study procedure. This includes AEs attributable to any device(s) other than the Barrel® VRD, Detachment Box, or Detachment Cables used at procedure (day 0), such as access devices, delivery microcatheters, embolic coils, non-ionic contrast, guidewires, or any other adjunctive, approved/cleared device for treatment of intracranial aneurysms.
- Device-related: Event has a strong temporal relationship to the study device (the Barrel® VRD, Detachment Box, or Detachment Cables), and alternative etiology is less likely.

All events considered “device-related” will be further characterized as either:

- Anticipated: When the event was previously identified in nature, severity or degree of incidence in the investigational plan. Or
- Unanticipated: When the event was not previously identified in nature, severity or degree of incidence in the investigational plan.
- Non-index procedure related: This includes AEs attributable to any device(s) used at procedures other than day 0, such as access devices, delivery microcatheters, non-ionic contrast, guidewires, or any other adjunctive, approved/cleared device for treatment of intracranial aneurysms.
- Antiplatelet therapy-related: Event is clearly attributable to antiplatelet therapy with no temporal relationship to the device, treatment, or medical history
- Unknown: Event relationship cannot be attributed to any of the above categories, and remains undetermined.

A **Stroke** is defined as a focal neurological deficit of presumed vascular origin persisting more than 24 hours from symptom onset AND a neuro-imaging study or other quantitative study that does not indicate a different etiology. The 24-hour criterion is excluded if the subject undergoes cerebrovascular surgery or dies during the first 24 hours.

The definition includes:

- Subjects presenting with clinical signs and symptoms suggestive of subarachnoid hemorrhage, intracerebral hemorrhage, or cerebral infarction.

The definition excludes:

- Slowly progressive cranial nerve palsies or progressive visual field deficits due to continued aneurysm growth.
- Stroke events in cases of blood disorders such as leukemia or external events such as trauma.
- Transient ischemic attacks, in which the symptoms resolve on their own within 24 hours

Stroke severity will be graded by the CEC as major or minor:

- Major Stroke: A stroke which increases the NIH Stroke Scale of the subject by  $\geq 4$ .
- Minor Stroke: A stroke which increases the NIH Stroke Scale of the subject by  $\leq 3$ .

The term “ipsilateral” in the primary safety endpoint definition will be defined as “on the same side of the brain as the target aneurysm” for MCA aneurysms and as “in the territory supplied by the treated artery” for basilar aneurysms.

Each stroke event will be adjudicated for “Ipsilateral” site of occurrence:

- Ipsilateral for MCA strokes
- In the territory supplied by the treated artery for Basilar artery strokes as adjudicated by the Clinical Events Committee

A **Neurological Death** is any subject death due to neurological reasons.

An **Intra-Cranial Hemorrhage (ICH)** is a hemorrhage within the fixed vault of the cranium (skull). These will be further categorized as:

- **Intra Cerebral Hemorrhage:**
  - Intra Ventricular Hemorrhage (IVH): Hemorrhage within the ventricles
  - Intra Parenchymal Hemorrhage (IPH): Bleeding within the cerebral matter (brain parenchyma), not involving the ventricles

\*Acute Ischemic Stroke with hemorrhagic transformations included in IPH will be explained in comments.
- **Sub Arachnoid Hemorrhage (SAH)**
  - A subarachnoid hemorrhage is bleeding into the subarachnoid space—the area between the arachnoid membrane and the pia mater surrounding the brain
- **Sub-Dural Hematoma (SDH)**
  - Subdural hematoma occurs when there is tearing of the bridging vein between the cerebral cortex and a draining venous sinus
- **Epidural Hematoma (EDH)**
  - A rapidly accumulating hematoma between the dura mater and the cranium

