#### 8.1.2 Secondary Endpoints

- Any cause death within 30 days or neurological death within 12 months  $\pm$  8 weeks.
- Number of Barrel® VRD treated aneurysms achieving Raymond Grade I or II at 12 months  $\pm$  8 weeks in the absence of retreatment, parent artery stenosis ( $> 50\%$ ), or target aneurysm rupture.
- Number and percentage of successful device implants
- Angiographic evidence of in-stent stenosis at 12 months  $\pm$  8 weeks reported according to the following ordinal groups:  $<25\%$ ,  $25-50\%$ ,  $51-75\%$ ,  $>75\%$ .
- Device-related Serious Adverse Events (SAEs).
- The composite percentage of patients with modified Rankin Score of 0-2 or no change from

baseline at 12 months  $\pm$  8 weeks.

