### 12.6.4 Post-placement Antiplatelet Agents

Antiplatelet agents will be given after the Barrel device placement procedure as defined below:

- Aspirin: At least 81 mg daily for a minimum of 12 months
- P2Y12 Platelet Inhibitor: Daily for a minimum of 3 months

Medications could be continued beyond above regimen if medically indicated.

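### The relatedness definitions add timing conditions to causal attribution: early drug-caused bleeds cannot literally be coded antiplatelet-related, one category contradicts itself, and late device effects are left open

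*Protocol*

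**What the plan says.** The Relatedness list in Protocol section 12.8.1 defines seven categories. Antiplatelet therapy-related reads: "Event is clearly attributable to antiplatelet therapy with no temporal relationship to the device, treatment, or medical history". Study Disease-related covers events clearly attributable to the aneurysm or to medications taken for it, "with no temporal relationship to the device, procedure, or concomitant medications". Device-related begins "Event has a strong temporal relationship to the study device" and ends "and alternative etiology is less likely". Procedure-related begins "Event has a strong temporal relationship to the study procedure" and then adds events attributable to ancillary devices used on day 0.

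Section 12.6.4 sets the regimen: "Antiplatelet agents will be given after the Barrel device placement procedure as defined below". Aspirin runs for at least 12 months and the P2Y12 inhibitor for at least 3 months.

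Earlier in section 12.8.1, an adverse device effect (ADE) is any adverse event related to use of the investigational device, with the note "This includes any adverse event resulting from insufficiencies or inadequacies in the instructions for use, the deployment, the implantation" and further items. It has no timing condition. The unanticipated adverse device effect (UADE) definition has none either.

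Device-related SAEs are a secondary endpoint (section 8.1.2), analysed descriptively (section 6.7). The Clinical Events Committee (CEC) adjudicates relatedness (section 14.8.7).

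**The concern.** Relatedness coding should separate harm from the implant, the procedure, the antiplatelet drugs and the disease. A timing condition added to a causal test can override a clear causal judgement. Here that matters most when a drug-caused bleed follows soon after placement, because drug exposure and the post-procedure period start together.

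If the definitions are followed as written, the antiplatelet row of the safety tables can be too low in the early period and the procedure or Unknown row too high. A late implant effect might also be left out of the device-related SAE endpoint. Only events considered device-related are then classed as anticipated or unanticipated under this list, so that classification carries the same exposure.

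**Working it through.** No arithmetic applies. The check sets out what each category in section 12.8.1 requires and then follows three kinds of event through the list.

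| Category | Causal condition | Timing condition |
|---|---|---|
| Study Disease-related | Clear attribution to the aneurysm or its medication | No relationship to device, procedure or concomitant medications |
| Concomitant disease-related | Clear attribution to the other disease or its medication | No relationship to device, procedure/treatment or study disease |
| Procedure-related | Attribution, only in the sentence on ancillary devices | Strong relationship to the procedure |
| Device-related | Other causes less likely | Strong relationship to the device |
| Non-index procedure related | Attribution to devices used at other procedures | None on the event itself |
| Antiplatelet therapy-related | Clear attribution to the drugs | No relationship to device, treatment or medical history |
| Unknown | Fits none of the above and stays undetermined | None |

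**Event 1: a bleed soon after placement, clearly caused by the antiplatelet drugs.**
- It meets the causal half of Antiplatelet-related. It fails the timing half, because it closely follows placement and section 12.6.4 starts the regimen at that point.
- Both disease categories carry the same kind of exclusion, so neither takes it.
- If its temporal relationship to the procedure is strong, it satisfies Procedure-related, whose opening sentence does not ask whether another cause is more likely.
- If the relationship exists but is not strong, it fails Antiplatelet-related (which demands none) and also Procedure-related and Device-related (which demand a strong one). Unknown is what remains, although the cause is in fact known.
- A non-serious bleed coded Unknown, without NIHSS worsening, is not on the section 14.8.7 list of events sent to the CEC. The same bleed coded antiplatelet-related would be.

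**Event 2: an event attributable to a medication taken for the aneurysm.**
- Study Disease-related includes it by cause.
- The same sentence excludes events with a temporal relationship to concomitant medications. An event caused by a medication will ordinarily have one, so the category removes what it has just included.

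**Event 3: a late effect of the implant, such as thrombosis or in-stent stenosis months after placement.**
- If the temporal relationship means closeness to implantation, the event fails Device-related.
- If it means that the device is in place, the event passes, subject to other causes being less likely.
- The text gives no window and no wording on delayed effects, so it does not settle which reading applies. Under the ADE and UADE definitions the question does not arise. One event could therefore be an ADE and yet not be device-related.

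**Where relatedness is used.** The primary efficacy endpoint depends on occlusion grade, retreatment, parent artery stenosis and rupture. The primary safety endpoint depends on neurological death and major ipsilateral stroke. Neither has a relatedness condition (section 8.1.1).

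**The case against.** The strongest reply has four parts.

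- **Most categories do test cause.** A reader might infer that the list codes by timing instead of cause. The table shows otherwise: only the first sentence of Procedure-related rests on timing alone. The fault is a timing condition laid on top of attribution. This part stands.
- **Late device effects may well be covered.** Procedure-related ties timing to the procedure and Device-related ties it to the device, which remains in the body. On that reading a late thrombosis qualifies, so a reader should not conclude that late events will be missed. This also stands, and it leaves an ambiguity at a named endpoint rather than a certain miscoding. Several late harms are also captured without relatedness: in-stent stenosis at 12 months is its own secondary endpoint, parent artery stenosis above 50% is an efficacy failure, and a major ipsilateral stroke counts for primary safety whatever its cause. Expedited reporting uses the UADE and USADE terms.
- **The exclusions may be deliberately conservative.** They stop peri-procedural events being explained away as drug or disease effects. That is a fair aim, but a comparison of likely causes serves it without barring a clear drug effect. The protocol also sends antiplatelet-related events to the CEC as a class of their own, which sits badly with a definition that shuts out the early ones.
- **The CEC is independent and sees every SAE.** This lowers the risk for serious events. It does not remove it, since the protocol gives the CEC no other relatedness definitions. The CEC charter is not shown and may add some.

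**Conclusion.** The point holds in three parts of unequal strength.

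- **Antiplatelet-related:** on a literal reading, an early bleed clearly due to the drugs cannot be coded here and goes to Procedure-related or Unknown. A reader might infer that all such bleeds become procedure-related, or that the problem covers the whole 3-month minimum of dual therapy. The text supports neither: Procedure-related needs a strong temporal relationship, and no window is given.
- **Study Disease-related:** the definition contradicts itself.
- **Device-related:** the wording is ambiguous for delayed effects and narrower than the ADE and UADE definitions. It could under-count late events; it is not shown that it will.

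The consequence is moderate. It reaches the descriptive device-related SAE endpoint, the relatedness tables and the anticipated/unanticipated classification of device-related events. It does not reach either primary endpoint. The protocol gives no event rates by relatedness category, so no number of affected events is claimed. The conclusion assumes that sites and the CEC apply section 12.8.1 as written. The change is still worth making, because these are stated rules that can miscode events when followed, and rewording them is cheap.

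**What to change.** In the Relatedness list of section 12.8.1:

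1. **Antiplatelet therapy-related:** replace the no-temporal-relationship exclusion with the limb that Device-related already has, "and alternative etiology is less likely", naming the device, the procedure and medical history as the alternatives. Add the same limb to Procedure-related; otherwise an early bleed could satisfy both categories.
2. **Study Disease-related:** delete the reference to concomitant medications from the exclusion clause.
3. **Device-related:** align it with the ADE definition by stating that events attributable to the presence, deployment or performance of the device qualify at any time after the attempt.

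Carry the wording into the CEC's working definitions. Apply it to all adjudicated events, not only to selected categories such as procedure-related bleeds or Unknown, since selective re-reading could itself introduce bias.

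Costs: some adjudication is repeated, and the device-related count may rise. Some early bleeds may move from procedure-related to antiplatelet-related, which lowers the procedure count. Report both counts so that the shift is visible. No new data collection is needed, and no treatment rule changes.
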